## **6. DOSING DELAYS/DOSE MODIFICATIONS**

Dose delays and modifications will be made as indicated in the following table(s). The descriptions and grading scales found in the revised NCI Common Terminology Criteria for Adverse Events (CTCAE) version 4.03 will be utilized for dose delays and dose modifications. A copy of the CTCAE version 4.03 can be downloaded from the CTEP website [http://ctep.cancer.gov/protocolDevelopment/electronic\\_applications/ctc.htm](http://ctep.cancer.gov/protocolDevelopment/electronic_applications/ctc.htm).

## 6.1 Eribulin Dosing Delays

- On day 1 or day 8 HOLD Eribulin administration if:
  - ANC  $\leq$ 1000/mm^3
  - Platelets  $\leq$  75,000/mm^3
  - CTCAE Grade 3 or 4 AE attributable to Eribulin with the specific exclusion of Grade 3 or 4 lymphopenia or Grade 3 hypophosphatemia, hypokalemia, hypocalcemia, or hypomagnesemia responsive to oral supplementation
- Day 1: If Eribulin cannot be administered on Day 1, the dose should be delayed until recovery to above these values. The Day 1 dose will be rescheduled for when the criteria for Eribulin administration are met. The dose of Eribulin must be reduced following a dose delay in accordance to the instructions for dose reduction.
- Day 8: If Eribulin cannot be administered on Day 8, the dose should be delayed until recovery to above these values. The Day 8 dose will be delayed for a maximum of 7 days
  - If the criteria above for Eribulin administration are met on, or before Day 15 of a cycle, administer Eribulin at a reduced dose according to section 6.2
  - Eribulin administration on Day 1 of the next cycle must be NO SOONER than 14 days later.
  - If the criteria above for Eribulin administration are NOT being met by Day 15 of a cycle, OMIT the Day 8 dose of Eribulin for that cycle and administer Eribulin at a reduced dose on Day 1 of the next scheduled cycle according to section 6.2.
- Clinical judgment will be used to determine appropriate management of the patient during any adverse event. Temporary interruption or permanent discontinuation of the study drug should be considered if clinically indicated.
- As long as the patient is deriving clinical benefit, there is no limit to the length of time Eribulin may be held.

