## 6.2 Instructions for Dose Reduction

- Do not re-escalate Eribulin dose after it has been reduced.
- Reduce the dose of Eribulin if any of the following values are present after the preceding dose:
  - Absolute Neutrophil Count  $<1,000/\text{mm}^3$  with fever and/or infection, or  $<500/\text{mm}^3$  for more than 7 days, despite use of growth factors
  - Platelet Count  $<50,000/\text{mm}^3$  requiring platelet transfusion, or  $<25,000/\text{mm}^3$
  - Possibly, probably or definitely related non-hematologic, clinically significant toxicity CTCAE Grade 3 or 4
  - Day 8 dose delay or omission due to treatment-related toxicity other than outlined above under neutropenia
  - Recurrence of any Grade 3 or 4 event despite reduction to 0.7 mg/m^2, consider discontinuation

Dose Level	Eribulin Dose
Dose 1	1.4 mg/m 
Dose -1	1.1 mg/m 

Dose -2	0.7 mg/m 
---------	-----------------------

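### Sections 6.1 and 6.2 do not agree clearly on which Day 1 and Day 8 toxicity holds lead to a dose reduction that cannot later be reversed

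*Combined protocol and SAP*

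**What the plan says.** Section 6.1 sets one set of hold criteria for both dosing days: ANC at or below 1,000/mm3, platelets at or below 75,000/mm3, or "CTCAE Grade 3 or 4 AE attributable to Eribulin with the specific exclusion of Grade 3 or 4 lymphopenia". The exclusions go on to cover certain Grade 3 electrolyte disturbances that respond to oral supplements. Anaemia is not excluded.

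The consequences in 6.1 depend on the day:

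- **Day 1.** The dose waits for recovery, and then "The dose of Eribulin must be reduced following a dose delay in accordance to the instructions for dose reduction".
- **Day 8, recovered by Day 15.** The instruction is to "administer Eribulin at a reduced dose according to section 6.2".
- **Day 8, not recovered by Day 15.** The dose is omitted and the next Day 1 dose is reduced, again by reference to 6.2.

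Section 6.2 opens its list with "Reduce the dose of Eribulin if any of the following values are present after the preceding dose". The triggers are:

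- ANC below 1,000 accompanied by fever or infection, or below 500 "for more than 7 days, despite use of growth factors";
- platelets below 50,000 needing transfusion, or below 25,000;
- for other toxicity, "Possibly, probably or definitely related non-hematologic, clinically significant toxicity CTCAE Grade 3 or 4", which leaves out hematologic events such as anaemia;
- for delays, one trigger only, worded as "Day 8 dose delay or omission due to treatment-related toxicity other than outlined above under neutropenia".

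A last bullet concerns recurrence at the lowest level. Section 6.2 also says "Do not re-escalate Eribulin dose after it has been reduced" and lists three levels: 1.4, 1.1 and 0.7 mg/m2.

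**The concern.** Section 6.1 sends the reader to 6.2 for the reduction, but the 6.2 triggers are narrower than the 6.1 hold criteria, and the only delay they name is on Day 8. A patient can therefore be held under 6.1, be told that the dose must come down, and match nothing in the list that is supposed to govern the reduction. On Day 8 the difficulty is different: an exception refers back to neutropenia without making clear how much of it is excepted.

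Two careful readers could give the same patient different doses after the same blood count, and the lower dose could not be raised again. In a 16-patient single-arm study, delivered dose would then depend partly on who read the protocol. Section 8.1.8 requires reductions and delays to be recorded, so delivered dose can be described afterwards. Recording does not settle which dose is to be given.

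**Working it through.** The plan gives no figure to reproduce here. The check applies each section's wording to the same holds. Each row assumes that no other trigger is present.

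| Reason for hold | Day 1, 6.1 alone | Day 1, 6.2 list | Day 8, 6.1 alone | Day 8, 6.2 list |
|---|---|---|---|---|
| ANC 800, no fever or infection | reduce | no trigger | reduce | depends on reading |
| ANC 400 for 5 days, no fever or infection | reduce | no trigger | reduce | depends on reading |
| ANC 800 with fever, growth factor in use | reduce | trigger | reduce | trigger |
| Platelets 60,000, treatment-related | reduce | no trigger | reduce | trigger |
| Platelets 40,000, treatment-related, no transfusion | reduce | no trigger | reduce | trigger |
| Platelets 20,000 | reduce | trigger | reduce | trigger |
| Attributable Grade 3 anaemia | reduce | no trigger | reduce | trigger |
| Related, clinically significant non-hematologic Grade 3 event, other than QTc prolongation | reduce | trigger | reduce | trigger |

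**Day 1.** The sections part in three groups: ANC holds that do not meet the ANC bullet; platelets of 50,000 to 75,000, or of 25,000 to below 50,000 without transfusion; and attributable Grade 3 or 4 anaemia. The text allows two readings. Either 6.1 creates its own trigger and takes only the dose levels from 6.2, or 6.1 defers to 6.2 and these patients are not reduced. Sections 5.1 and 5.4 refer to section 6 as a whole and set no precedence. The clinical-judgment bullet in 6.1 concerns management, interruption and discontinuation.

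**Day 8.** If the exception in "Day 8 dose delay or omission due to treatment-related toxicity other than outlined above under neutropenia" covers every neutropenia delay, an uncomplicated ANC hold is not reduced under 6.2 but is reduced under 6.1. If it covers only the events already in the ANC bullet, both sections reduce and there is no conflict. Treatment-related platelet and anaemia delays agree on either reading.

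**Outside the point.** Non-clinical delays are dealt with in section 10. Grade 3 or 4 QTc prolongation goes to discontinuation under 6.3.

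**Size of one disputed hold.**

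- From 1.4 mg/m2: 1.1 / 1.4 = 0.786, so 79% of the dose; per two-dose cycle, 2 × 1.4 = 2.8 against 2 × 1.1 = 2.2 mg/m2.
- From 1.1 mg/m2: 0.7 / 1.1 = 0.636, so 64% of the dose; per cycle, 2.2 against 2 × 0.7 = 1.4 mg/m2.
- From 0.7 mg/m2: no lower level is listed, so no one-level difference arises.

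**How long it lasts.** Suppose one reader reduces to 1.1 and the other stays at 1.4. After one later undisputed reduction they are at 0.7 and 1.1. After a second, both are at 0.7, unless treatment has stopped by then. A gap of 1.1 against 0.7 closes after one.

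**The case against.** The best answer is that both sections can be followed together. Section 6.2 says to reduce if any listed event is present; it does not say only if. On this view 6.1 governs counts on the dosing day, while 6.2 adds events seen since the preceding dose and supplies the levels. The introduction to section 6 says that modifications follow its tables, and the only table shown in 6.1 and 6.2 lists dose levels, which supports reading the cross-reference as a pointer to the next level down. Day 1 then has an incomplete list and no contradiction.

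This reading is possible, but it does not settle the matter. If every 6.1 hold already leads to reduction, most of the Day 8 bullet in 6.2 is redundant, and a reader has reason to doubt that this was meant. The opposite reading, in which 6.2 governs, leaves the Day 1 sentence in 6.1 adding nothing, because the 6.2 triggers apply anyway. Nothing in the text chooses between the two.

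Four limits raised against the point do stand:

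- Agreement on Day 8 platelet holds is confined to treatment-related events, since 6.1 applies no attribution test to counts and the 6.2 bullet does.
- It would be wrong to say that all related, clinically significant non-hematologic Grade 3 or 4 toxicity leads to reduction, because 6.3 treats QTc prolongation separately.
- A reader might infer that the dose difference lasts for the rest of treatment. It need not, because 0.7 mg/m2 is the lowest listed level and the two courses can meet there.
- Section 5.1 provides prophylactic growth factor by national guideline or institutional standard, which may limit the disputed neutropenia holds.

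**Conclusion.** The point holds as an unresolved inconsistency in a rule that the trial acts on, and it should be fixed. On Day 1 it covers uncomplicated neutropenia, the two platelet ranges above and attributable Grade 3 or 4 anaemia. On Day 8 it comes down to how far the neutropenia exception reaches. Each disputed hold is worth one dose level where a lower level is listed. That level cannot be regained by re-escalation, though the gap may close.

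Two stronger conclusions are not supported. A reader might take the 51.9% rate of Grade 3 or 4 neutropenia in the soft tissue sarcoma study cited in section 2.2.3 to mean that about half the patients would be affected (16 × 0.519 = 8.3). That figure counts patients with the event at any time; it is not a rate of holds on a dosing day, and the documents give no such rate. A reader might also infer that the response analysis is compromised. Sample size, power and the rule of at least 4 responses in 16 do not depend on these sections, and the documents quantify no effect of dose on response.

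The conclusion rests on the wording alone. It takes no view on which patients should be reduced.

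**What to change.** Reconcile 6.1 and 6.2 into a single list that states, separately for Day 1 and Day 8, which delays or omissions trigger a reduction: neutropenia, platelets, other hematologic events and non-hematologic events. The list should say which neutropenia delays, if any, are exempt and whether attribution to treatment is required. Section 6.1 should then refer to that list and carry no separate statement of the consequence.

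As minor tidying, align the hold limits: sections 5.3 and 5.4 hold below 1,000 and 75,000, while 6.1 holds at or below them, so they differ only at exactly those values.

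The sponsor and the investigator decide which rule applies. The cost is amendment wording, with no change to sample size, endpoints or data collection.

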## 6.2 Instructions for Dose Reduction

- Do not re-escalate Eribulin dose after it has been reduced.
- Reduce the dose of Eribulin if any of the following values are present after the preceding dose:
  - Absolute Neutrophil Count  $<1,000/\text{mm}^3$  with fever and/or infection, or  $<500/\text{mm}^3$  for more than 7 days, despite use of growth factors
  - Platelet Count  $<50,000/\text{mm}^3$  requiring platelet transfusion, or  $<25,000/\text{mm}^3$
  - Possibly, probably or definitely related non-hematologic, clinically significant toxicity CTCAE Grade 3 or 4
  - Day 8 dose delay or omission due to treatment-related toxicity other than outlined above under neutropenia
  - Recurrence of any Grade 3 or 4 event despite reduction to 0.7 mg/m^2, consider discontinuation

Dose Level	Eribulin Dose
Dose 1	1.4 mg/m 
Dose -1	1.1 mg/m 

Dose -2	0.7 mg/m 
---------	-----------------------

### **6.3 Instructions for QTc Interval Prolongation**

- QTc prolongation has been observed in patients receiving Eribulin. ECG monitoring is required for screening, and day 1 for cycle 2 and 3. It is recommended to continue day 1 monitoring beyond cycle 3 for subjects during the treatment who have:
  - Grade 2 QTc interval prolongation
  - Clinically relevant electrolyte abnormalities
  - Bradyarrhythmias and/or congestive heart failure
  - Coadministration of medicinal products known to prolong the QT interval, including Class Ia and III anti-arrhythmics
- For subjects who develop Grade 3 or Grade 4 QTc interval prolongation, discontinue Eribulin and monitor ECGs and electrolytes frequently until the QTc interval returns to baseline. If a reversible etiology not related to Eribulin is determined to be the cause of the QTc interval prolongation rechallenge may be considered after discussion with the overall PI and resolution to grade 2 or better QTc interval prolongation.

### **6.4 Instructions for Peripheral Neuropathy**

Grade 3 and 4 peripheral neuropathy has been observed in patients receiving Eribulin. Patients should be monitored for signs of neuropathy. For patients with grade 3 or 4 peripheral neuropathy Eribulin should be held until improvement to Grade 2 or better. Dose reductions apply as per section 6.2.

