## **2.3 Rationale**

Clinical data has demonstrated that AS is sensitive to taxanes.(18-22) Indeed at our institution first line therapy is paclitaxel or gemcitabine with taxotere. However, all patients with advanced disease will eventually progress.

Eribulin, a novel microtubule-depolymerizing drug has shown clear activity in metastatic breast and sarcoma patients, despite failure of prior taxanes in many of these patients.

There is now emerging evidence in breast cancer models that Eribulin induces tumor vasculature remodeling as well as altering angiogenesis signaling pathways involved in endothelial cell-pericyte interactions as well as VEGF expression.(12) Moreover, there is further evidence of the Eribulin-mediated vascular remodeling hypothesis in PDX and human breast cancer patients where Eribulin can decreases tumor hypoxia.(23)

In addition to the above there are now anecdotal reports as well as a published report of angiosarcoma patients responding to Eribulin.(24)

Together these data suggest Eribulin's anti-tumor activity is through multiple mechanisms including microtubule targeting, alterations in angiogenesis signaling/vasculature remodeling and tumor hypoxia changes. Thus, we hypothesize that Eribulin will show anti-cancer activity in vascular malignancies including angiosarcoma and progressing epithelioid hemangioendothelioma.

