### **3. PARTICIPANT SELECTION**

#### **3.1 Eligibility Criteria**

- 3.1.1 Metastatic or locally advanced angiosarcoma, treated with at least one prior systemic therapy where no standard of care curable therapy is available OR metastatic or locally advanced malignant and progressive epithelioid hemangioendothelioma (EHE).
  - 3.1.1.1 A maximum of 5 EHE patients will be accrued on this study
- 3.1.2 Archival tissue confirming the diagnosis must be reviewed by BWH/DFCI/MGH pathology.
- 3.1.3 Progression on at least one prior systemic therapy or progression during an observation phase of no anti-cancer therapy within the prior 3 months; prior taxanes are allowed

3.1.4 Participants must have measurable disease by RECIST 1.1, defined as at least one lesion that can be accurately measured in at least one dimension (longest diameter to be recorded for non-nodal lesions and short axis for nodal lesions) as  $\geq 20$  mm with conventional techniques or as  $\geq 10$  mm with spiral CT scan, MRI, or calipers by clinical exam. See Section 11 for the evaluation of measurable disease.

3.1.5 Age  $\geq 18$  years.

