3.1.6 ECOG performance status  $\leq 2$  (see Appendix A)

3.1.7 Life expectancy of greater than 3 months

3.1.8 Participants must have normal organ and marrow function as defined below:

- leukocytes	$\geq 3,000/\text{mcL}$
- absolute neutrophil count	$\geq 1,000/\text{mcL}$
- platelets	$\geq 100,000/\text{mcL}$
- total bilirubin	within normal institutional limits
- AST(SGOT)/ALT(SGPT)	$\leq 2.5 \times$ institutional upper limit of normal
- creatinine clearance	$\geq 50 \text{ mL/min}/1.73 \text{ m}^2$ for participants with creatinine levels above institutional normal.

3.1.9 Baseline QTcF  $<$  grade 2

3.1.10 The effects of Eribulin on the developing human fetus are unknown (Please also see exclusion criteria 3.2.6). For this reason and because of the risk of teratogenicity, women of child-bearing potential must agree to use adequate contraception prior to study entry and for the duration of study participation, and 4 months after completion of Eribulin administration. Should a woman become pregnant or suspect she is pregnant while she or her partner is participating in this study, she should inform her treating physician immediately. Men treated or enrolled on this protocol must also agree to use adequate contraception prior to the study, for the duration of study participation, and 4 months after completion of Eribulin administration. Please see section 5.6 for complete details on contraception.

3.1.11 Willingness to undergo serial tumor biopsies before and on treatment.

3.1.12 Ability to understand and the willingness to sign a written informed consent document.

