## 3.2 Exclusion Criteria

- 3.2.1 Participants who have had chemotherapy or radiotherapy within 3 weeks (6 weeks for nitrosoureas or mitomycin C), immunotherapy within 3 weeks, targeted therapies (e.g. small molecule inhibitors such as pazopanib) within 2 weeks prior to entering the study or those who have not recovered from adverse events due to agents administered more than 4 weeks earlier. Not clinically significant or clinically stable adverse events from prior therapy (e.g. immunotherapy related hypothyroidism or insulin-dependent diabetes stable on medication or TKI-related hypertension or rash etc.) is allowed.
- 3.2.2 Participants who are receiving any other investigational agents.
- 3.2.3 Participants with with brain or subdural metastases are not eligible, unless they have completed local therapy and have discontinued the use of corticosteroids for this indication for at least 4 weeks before starting treatment in this study. Any signs (e.g. radiologic) or symptoms of brain metastases must be stable for at least 4 weeks before starting study treatment. Participants with leptomeningeal disease should be excluded from this clinical trial because of their poor prognosis and because they often develop progressive neurologic dysfunction that would confound the evaluation of neurologic and other adverse events.
- 3.2.4 History of allergic reactions attributed to compounds of similar chemical or biologic composition to eribulin.
- 3.2.5 Uncontrolled intercurrent illness including, but not limited to, ongoing or active infection, symptomatic congestive heart failure (NYHA Class II), unstable angina pectoris or myocardial infarction within 6 months of enrollment, serious or life-threatening cardiac arrhythmia, subjects with a high probability of Long QT syndrome or QTcF prolongation of  $\geq 501$  msec (grade 2) on at least two separate ECG following correction of any electrolyte imbalance or psychiatric illness/social situations that would limit compliance with study requirements.
- 3.2.6 Females who are breastfeeding or pregnant at Screening or Baseline (as documented by a positive beta-human chorionic gonadotropin [ $\beta$ -hCG] (or human chorionic gonadotropin [hCG]) test with a minimum sensitivity of 25 IU/L or equivalent units of  $\beta$ -hCG (or hCG)). A separate baseline assessment is required if a negative screening pregnancy test was obtained more than 72 hours before the first dose of study drug.

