**15. APPENDIX A PERFORMANCE STATUS CRITERIA**

ECOG Performance Status Scale		Karnofsky Performance Scale	
Grade	Descriptions	Percent	Description
0	Normal activity. Fully active, able to carry on all pre-disease performance without restriction.	100	Normal, no complaints, no evidence of disease.
		90	Able to carry on normal activity; minor signs or symptoms of disease.
1	Symptoms, but ambulatory. Restricted in physically strenuous activity, but ambulatory and able to carry out work of a light or sedentary nature (e.g., light housework, office work).	80	Normal activity with effort; some signs or symptoms of disease.
		70	Cares for self, unable to carry on normal activity or to do active work.
2	In bed <50% of the time. Ambulatory and capable of all self-care, but unable to carry out any work activities. Up and about more than 50% of waking hours.	60	Requires occasional assistance, but is able to care for most of his/her needs.
		50	Requires considerable assistance and frequent medical care.
3	In bed >50% of the time. Capable of only limited self-care, confined to bed or chair more than 50% of waking hours.	40	Disabled, requires special care and assistance.
		30	Severely disabled, hospitalization indicated. Death not imminent.
4	100% bedridden. Completely disabled. Cannot carry on any self-care. Totally confined to bed or chair.	20	Very sick, hospitalization indicated. Death not imminent.
		10	Moribund, fatal processes progressing rapidly.
5	Dead.	0	Dead.

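### No entry limit on baseline peripheral neuropathy: a patient with stable grade 3 neuropathy after a taxane can be judged eligible, although Section 6.4 says to hold eribulin at that grade

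*Combined protocol and SAP*

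**What the plan says.** All references are to the combined protocol and SAP.

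- **Hold rule.** Section 6.4 notes that grade 3 and 4 peripheral neuropathy has occurred on eribulin, and continues: "For patients with grade 3 or 4 peripheral neuropathy Eribulin should be held until improvement to Grade 2 or better". It does not restrict the rule to neuropathy caused by eribulin.
- **Prior treatment.** Section 3.1.1 requires angiosarcoma patients to have had prior systemic therapy. Section 3.1.3 adds that "prior taxanes are allowed". Section 2.3 describes local practice: "Indeed at our institution first line therapy is paclitaxel or gemcitabine with taxotere". Section 3.1.1.1 limits the other disease group: "A maximum of 5 EHE patients will be accrued on this study".
- **Residual toxicity at entry.** Section 3.2.1 excludes "those who have not recovered from adverse events due to agents administered more than 4 weeks earlier". It then makes an exception: "Not clinically significant or clinically stable adverse events from prior therapy" are allowed. The examples are endocrine conditions stable on medication, hypertension and rash. The list is open-ended and has no grade ceiling.
- **Hold rules around the first dose.** The Cycle 1 Day 1 list in Section 5.3 names only neutrophils and platelets. The lists for later doses (Sections 5.4 and 6.1) add grade 3 or 4 events, but only those attributed to eribulin.
- **Baseline grading.** Section 5.2 has pre-existing conditions graded by CTCAE v4.03 and attaches no eligibility threshold to the result.

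**The concern.** The drug has a known neurotoxicity, and the protocol has chosen grade 3 as the point at which dosing should stop. Entry is not tied to that point. A patient can arrive already at grade 3 from an earlier taxane, be classed as stable, and pass every written criterion.

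The patient may then undergo a research biopsy for a drug that is held on the day it was due to start, possibly for good. Alternatively, a patient whose neuropathy is already at the protocol's stopping grade receives a further neurotoxic dose. The trial's inference is not at stake.

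**Working it through.** The plan gives no figure for baseline neuropathy, so there is none to reproduce. The check is a reading of the text, followed by one small calculation under stated assumptions.

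**Step 1: can the patient enter?** Take an angiosarcoma patient with stable grade 3 neuropathy from a taxane given more than four weeks earlier.

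- Prior taxane: allowed (3.1.3).
- Unrecovered adverse event: excluded by default (3.2.1), but the same item excepts stable events at any grade. The examples do not settle whether neuropathy belongs among them.
- Performance status: ECOG 2 or better is required (3.1.6). Appendix A describes grade 2 as "Ambulatory and capable of all self-care, but unable to carry out any work activities", among other wording. This may screen out some such patients. The documents do not reproduce the CTCAE definition of grade 3 neuropathy, so it cannot be shown to exclude them.
- Neurological criteria: Section 3.2.3 concerns brain and leptomeningeal disease, not peripheral nerves.

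Entry therefore depends on how the investigator reads the exception. No text requires exclusion.

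**Step 2: what happens after registration?** Biopsy 1 is required after registration and before Cycle 1 Day 1 (5.3). It can be waived only if considered unsafe (Section 10, footnote F). Two outcomes then fit the text:

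| Reading | Basis | Consequence |
|---|---|---|
| 6.4 applies to every dose | 5.1 refers to Section 6 for dose modifications; 6.4 is worded without limit | Held on Cycle 1 Day 1: registered and probably biopsied, but not dosed |
| Section 6 applies from Cycle 1 Day 8 | 5.4 refers to Section 6; the 5.3 list has only blood counts | One dose at grade 3, then a hold |

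The attribution-limited holds in 5.4 and 6.1 do not catch neuropathy left by an earlier drug. Only 6.4 does.

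**Step 3: how many patients could be affected?** With at most 5 EHE patients among 16, at least 16 − 5 = 11 are angiosarcoma patients with prior systemic therapy. That therapy need not have been a taxane, although Section 2.3 makes one likely for patients treated first-line at this institution. That a taxane can leave stable grade 3 neuropathy is itself an assumption here, and the documents give no prevalence q. For assumed values, the chance of at least one case among 11 is 1 − (1 − q)^11:

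| Assumed q | 1 − (1 − q)^11 |
|---|---|
| 0.5% | 1 − 0.995^11 ≈ 5% |
| 1% | 1 − 0.99^11 ≈ 10% |
| 2% | 1 − 0.98^11 ≈ 20% |
| 5% | 1 − 0.95^11 ≈ 43% |

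If no EHE patient enrolled and all 16 were previously treated, the same formula with exponent 16 gives 8%, 15%, 28% and 56%. Both sets overstate the event that matters, because the investigator must also decide to enrol the patient.

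**Step 4: the primary result.** A dosed patient counts in the response analysis (13.6.2). An undosed patient has the registration cancelled (4.1). Both outcomes are already provided for, and neither the analysis rule nor the decision rule changes.

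**The case against.** The best defence has four parts.

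1. **The default is exclusion.** The exception's examples are mostly controlled or mild conditions, and grade 3 neuropathy does not sit naturally beside them. Enrolment would also be a knowing decision, since Section 5.2 grades the neuropathy, Section 4.1 has an investigator confirm eligibility, and Section 5.3 requires certification of every criterion. This stands and is why the event is probably rare. It does not close the gap, because the exception as written permits the opposite judgment.

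2. **Section 6.4 is an on-treatment rule, and a hold threshold need not equal an entry threshold.** It sits among the dose modifications and points to Section 6.2, which acts on what happened after the preceding dose. QTc illustrates the second half: Section 3.1.9 ("Baseline QTcF" below grade 2) is stricter than the grade 3 or 4 action point in Section 6.3. So QTc is a precedent only for having an entry limit, not for where to set it. But if 6.4 does not govern the first dose, the patient is dosed at grade 3, which makes an entry limit more useful.

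3. **Harm is bounded.** Under the literal reading no drug is given, and under the other a single dose is. Section 6.1 also leaves room for clinical judgment. This stands and keeps the point small.

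4. **Judgment rather than a fixed grade is a legitimate choice** in a rare, aggressive disease. That is fair in general. Here, however, an exception applied as written can admit a patient whom the protocol's own rule says not to dose.

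A reader might go further and infer that dosing could continue indefinitely at grade 3, on the view that 6.4, like 6.1 and 6.2, concerns only eribulin-related toxicity. The documents do not support relying on that: 6.4 has no attribution wording, and the limit would have to be imported from neighbouring sections.

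**Conclusion.** The gap is real and minor. The stability exception in 3.2.1, read as written, can admit a patient whom 6.4 says should not be dosed, and no entry criterion or Cycle 1 Day 1 rule clearly prevents it. The consequence is an avoidable research biopsy or at least one avoidable neurotoxic dose, in a probably very small number of patients.

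This rests on two assumptions from outside the documents: that prior taxanes can leave stable grade 3 neuropathy, and the illustrative prevalences of 0.5% to 5%. It also supposes that an investigator would class such neuropathy as stable and enrol the patient.

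A reader might infer that the trial's power or type I error is compromised. That does not follow. Any such figure needs an assumption about whether an affected patient could respond, and the documents give no basis for one. With so few patients likely to be affected, the effect on the primary result is negligible.

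**What to change.** Add to Section 3.2 an exclusion for peripheral neuropathy of CTCAE v4.03 grade 3 or higher at baseline, which is the threshold already used in 6.4. Add a clause to 3.2.1 stating that the exception for stable adverse events does not override it. Both readings in the working then give the same answer, because the patient is identified before registration and biopsy.

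The cost is one line and one clause. No new assessment is needed, because Section 5.2 already grades pre-existing conditions on the same scale. Patients with grade 1 or 2 neuropathy are unaffected by the new limit. The downside is that an occasional patient with an aggressive disease is screened out; under the literal reading of 6.4, that patient would not have been dosed while at grade 3.
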